5.4.2. Exclusion criteria

HCPs meeting any of the following criteria will not be included in the survey:

- HCPs who are not involved in the management of patients with diabetes
- HCPs who have ever worked for or who have had family members who have ever worked for Lilly, UBC, or the FDA will be excluded.

Patients meeting any of the following criteria will not be included in the survey:

- Patients with diabetes who have not been prescribed Humalog U-200 KwikPen
- Patients who have ever worked for or who have had family members who have ever worked for Lilly, UBC, or the FDA will be excluded.

5.5. Variables

The surveys will collect participants' understanding of the key safety messages in the risk minimization communication and information about potential behavior. Additionally, the HCP survey will collect information on demographic characteristics that include age, gender, geographical location, HCP specialty, and practice information. HCP-identifying information will be collected for the purposes of providing payment for participation where applicable. The patient survey will collect a variety of respondent demographic characteristics that include age, gender, geographical location, and their length of experience with any insulin therapy and Humalog U-200 KwikPen.

5.6. Data sources

In this survey, the data source for HCPs will be Lilly's list of HCPs who received the DHPC. From this data source HCPs will be invited to participate in the survey. The data source for patients will be the PBM's prescription data identifying those patients who have filled/refilled a prescription of Humalog U-200 KwikPen within 90 days prior to survey launch.

Structured questionnaires ([APPENDIX I.1](#) and [APPENDIX I.3](#)) comprised of closed-ended questions or statements with multiple response choices (i.e., questions or statements asking the respondents to choose from a defined list of responses) will be used to collect the survey data. The surveys will collect data on respondent characteristics and their responses to the risk understanding questions. The data collected from the surveys will be used to inform the evaluation of the effectiveness of the risk minimization measures.

Each survey will begin with a screening module with questions to confirm eligibility. Depending on the answers to the screening questions, survey participation will either be terminated or continued. If ineligible, the respondent is immediately notified with a "thank you" message that survey participation has ended. If eligible, the respondent is allowed to continue survey participation.

HCPs:

Screening questions:

- Agreement to participate
- Involved in the management of patients with diabetes
- Employment by Lilly, UBC, or the FDA
- Awareness of Humalog U-200 KwikPen

Data on demographic characteristics:

- Age
- Gender
- Role at facility
- Facility type
- State of practice

- HCP medical specialty (e.g., endocrinology, primary care)
- Number of years practicing medicine/nursing
- Number of Humalog U-200 KwikPen-treated patients the HCPs prescribed to or managed in the 12 month period preceding the survey (self-reported)

Data pertaining to evaluation of the effectiveness of the risk minimization measures:

The survey includes questions/statements that will assess the understanding or the risks and associated behavior of the HCPs to minimize these risks. The understanding level and behaviors will be analyzed using descriptive statistics and confidence intervals (CIs) and will be used to determine the effectiveness of the risk minimization measures:

- Awareness of the DHPC on the correct use of Humalog U-200 KwikPen
- Understanding of the key safety messages
- Self-reported practices with respect to communication of the key safety messages in clinical practice

Patients:

Screening questions:

- Agreement to participate
- Diagnosis of diabetes
- Filled a prescription for Humalog U-200 KwikPen within the past 90 days prior to survey launch
- 18 years or older
- Employment by Lilly, UBC, or the FDA

Data on demographic characteristics:

- Age
- Gender
- State
- Employment status
- Length of time with diabetes
- Length of time on any insulin therapy
- Length of time on Humalog U-200 KwikPen
- Length of time on mealtime Insulin used prior to Humalog U-200 KwikPen

Data pertaining to evaluation of the effectiveness of the risk minimization measures:

The survey includes questions/statements that will assess the risk understanding and behavior of patients. The understanding level and behaviors will be analyzed using descriptive statistics and CIs and will be used to determine the effectiveness of the risk minimization measures:

- Awareness of the Important Safety Information for Humalog U-200 KwikPen
- Receipt of or access to the Important Safety Information
- Understanding of the key safety messages
- Behavior with respect to the key safety messages

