5.3. Study Endpoints

The additional Risk Minimization Measures will be considered effective if the majority of respondents demonstrate they are aware of the key safety messages communicated.

HCPs:

- Demonstrating that they understand the key safety messages communicated in the DHPC.
- Reporting they discuss the safe use of the product as defined in the product label and DHPC to their patients who are receiving their first prescription of Humalog U-200 KwikPen.

Patients:

- Demonstrating that they understand the key safety messages communicated about Humalog U-200 KwikPen.
- Reporting that they follow the key safety messages during administration of Humalog U-200 KwikPen.

All statistical analyses will be descriptive, i.e., no formal hypothesis will be tested.

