Eligible patients will receive an invitation letter ([APPENDIX I.4](#)) mailed by the PBM directly to the patient via the USPS. The invitation letter will indicate that participants will be compensated \$20 for their time and effort in completing the survey and will also include an overview of the rationale for the survey, information on how to access the survey online and by telephone, and a unique User Identification to ensure that the invitation is used only once. For telephone interviews, a trained interviewer, working from a CATI script, will read questions or statements to the patient. The letter will also contain a unique code that the respondent must provide when accessing the survey via the Internet or telephone. The average survey is expected to take approximately 15 minutes to complete.

The response rate will be monitored throughout the data collection period. If necessary, reminder notices will be sent to patients who have been invited to participate but have not responded. Additional recruitment methods may be explored prior to and or during survey launch if necessary to achieve a total of 280 completed surveys.

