5.4.1. Inclusion criteria

HCPs must meet the following criteria to be eligible for inclusion in the survey:

- HCPs are aware of the insulin product Humalog U-200 KwikPen; and
- HCPs are involved in the treatment and management of patients with diabetes.

Patients must meet all of the following criteria to be eligible for inclusion in the survey:

- Patients are 18 years or older;
- Patients have diabetes; and
- Patients have filled at least one (1) prescription of Humalog U-200 KwikPen within the past 90 days.

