APPENDIX I.3 PATIENT SURVEY

SURVEY LEGEND

- **[PROGRAMMER]** is used to indicate directions to the programmer and is set in bold, red, uppercase letters between square brackets.
- **(INTERVIEWER)** is used to indicate directions to the telephone interviewer and is set in bold, blue, text between parentheses. This text appears when content is to be administered by telephone only (for example, spontaneous safety event reporting).
- **[ONLINE]** indicates a question/section is worded specifically for administering the survey online.
- **[TELEPHONE]** indicates a question/section is worded specifically for administering the survey over the telephone.
- **[BEGIN <Section>]** and **[END <Section>]** are used to indicate to the programmer the beginning and end of the survey or sections of text within the survey, for example, **[BEGIN PHONE PREAMBLE 1]** and **[END PHONE PREAMBLE 1]**.
- **[TERMINATE]** is displayed next to responses that should cause the survey to end. The following termination language will be programmed into the survey or read by the interviewer.

Thank you very much for your time today. Based on your answer, you are not eligible to take this survey. We appreciate your interest in the survey.
- **[RANDOMIZE LIST]** is inserted before questions to indicate to the programmer that the responses should be randomized. Responses such as “I don’t know,” “Prefer not to answer” or “None of the above” will always appear at the end of the randomized responses.
- **[GO TO Qx]** (skip logic) is inserted after a response to indicate to the programmer that the survey should skip to the indicated question (for example, **[GO TO Q17]** skips to question 17). If no skip logic is indicated the survey continues to the next question in the sequence.
- **[MULTILINE INPUT]** indicates to the programmer that multiple lines should be provided for data entry (for example, two address lines).
- **[FREE TEXT]** indicates to the programmer that one line should be provided for data entry.

SURVEY LEGEND

- **[DROP-DOWN LIST INPUT WITH STATES TABLE]** indicates to the programmer that the response should be a drop-down list containing the states in the table below.

Alabama	Georgia	Massachusetts	New York	Tennessee
Alaska	Hawaii	Michigan	North Carolina	Texas
Arizona	Idaho	Minnesota	North Dakota	Utah
Arkansas	Illinois	Mississippi	Ohio	Vermont
California	Indiana	Missouri	Oklahoma	Virginia
Colorado	Iowa	Montana	Oregon	Washington

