 - More than 15 years
 - I don't know

5. Do you use injectable insulin to treat your diabetes?
- Yes
 - No **[GO TO Q10, TERMINATE AFTER Q14]**
 - I don't know **[GO TO Q10, TERMINATE AFTER Q14]**
 - I don't have diabetes **[GO TO Q10, TERMINATE AFTER Q14]**
6. For how long have you been using injectable insulin to manage your diabetes?
- Less than 1 year
 - 1 – 5 years
 - 6 – 10 years
 - 11 – 15 years
 - More than 15 years
 - I don't know **[GO TO Q10, TERMINATE AFTER Q14]**
7. Have you been prescribed Humalog® U-200 KwikPen® at least once?
- Yes
 - No **[GO TO Q10, TERMINATE AFTER Q14]**
 - I don't know **[GO TO Q10, TERMINATE AFTER Q14]**
 - I don't have diabetes/I don't use insulin **[GO TO Q10, TERMINATE AFTER Q14]**

8. For how long have you been using Humalog® U-200 KwikPen®?
- I have not used the Humalog® U-200 KwikPen® yet
 - Less than 3 months
 - 3 – 6 months
 - 7 – 12 months
 - More than 1 year
 - I don't know
 - I don't have diabetes/I don't use Humalog® U-200 KwikPen® **[GO TO Q10, TERMINATE AFTER Q14]**
9. What type of mealtime insulin did you use prior to using Humalog® U-200 KwikPen®?
- Humalog® U-100 KwikPen®
 - Other 100 Units/mL insulin
 - I don't know
 - I don't have diabetes/I don't use Humalog® U-200 KwikPen® **[TERMINATE AFTER Q14]**
10. What is your gender?
- Male
 - Female

11. What is the highest level of education you have completed?

- Less than high school
- Some high school
- High school graduate/GED (General Education Diploma)
- Some college/Associate's degree
- Bachelor's degree
- Master's degree
- Professional or Doctoral degree
- Prefer not to answer

12. In what state do you live?

[DROP-DOWN LIST INPUT WITH STATES TABLE, EXCLUDE PREFER NOT TO ANSWER]

13. Which of the following groups best describes your age?

- Under 18 **[TERMINATE AFTER Q14]**
- 18 – 29
- 30 – 39
- 40 – 49
- 50 – 59
- 60 – 69
- 70 or older
- Prefer not to answer **[TERMINATE AFTER Q14]**

14. Have you or any of your immediate family members ever worked for Eli Lilly and Company (Lilly), United BioSource Corporation (UBC), or the Food and Drug Administration (FDA)?
- Yes **[TERMINATE]**
 - No
 - I don't know **[TERMINATE]**

[END SCREENING QUESTIONS]

[BEGIN SURVEY CONTENT]

[BEGIN PREAMBLE 2 – DISPLAY ON SAME PAGE AS NEXT QUESTION]

The following questions are about Humalog® U-200 KwikPen®.

[END PREAMBLE 2]

15. Please answer True, False, or I don't know for each of the following statements about Humalog® U-200 KwikPen®.

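### The patient survey asks people who have not yet used the pen how they behave when injecting, so the patient behaviour endpoint mixes users with never-users

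*Protocol*

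**What the plan says.** **Endpoint.** Protocol Section 5.3 gives the patient behaviour endpoint as "Reporting that they follow the key safety messages during administration of Humalog U-200 KwikPen".

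**Survey flow.** In Appendix I.3, question 8 (duration of use) includes the answer "I have not used the Humalog® U-200 KwikPen® yet" with no instruction beside it. The legend to that appendix states: "If no skip logic is indicated the survey continues to the next question in the sequence". Item 16C asks whether the respondent thinks of the safety information at the time of injecting. It has no display condition and offers only Yes, No and I don't know. Section 5.11.1 requires an answer to every question presented. The patient correct-answer document at the end of Appendix I.3 keys 16C as Yes, and Section 5.9 counts I don't know on key-message questions as incorrect unless otherwise specified.

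**Eligibility.** Section 5.4.1 requires "Patients have filled at least one (1) prescription of Humalog U-200 KwikPen within the past 90 days". Section 5.6 says "Each survey will begin with a screening module with questions to confirm eligibility" and lists among the patient screening questions "Filled a prescription for Humalog U-200 KwikPen within the past 90 days prior to survey launch". It also names PBM prescription data for the same window as the patient data source. The closest question in the survey is question 7, "Have you been prescribed Humalog® U-200 KwikPen® at least once".

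**The concern.** Someone who has filled a prescription but not yet injected from the pen has no conduct with it to report. Item 16C is the only patient item worded as conduct while injecting; 16D and 16E, on the backup pen and syringe transfer, read as knowledge items. The patient side of the secondary objective therefore leans heavily on 16C. If never-users answer No or I don't know, the communication appears to fail in people who have had no occasion to act on it. If they answer Yes, the result is an intention recorded as behaviour. Either way the pooled percentage no longer describes behaviour during administration.

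Separately, a criterion that the protocol says is confirmed by a screening question is not asked, so the protocol text and the instrument disagree on how eligibility is established.

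**Working it through.** **1. Route of a never-user through Appendix I.3.**

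- Question 7: ever prescribed, so the respondent continues.
- Question 8: not used yet, with no exit marked, so the respondent continues under the legend's default.
- Question 9 (previous mealtime insulin): a respondent who names the earlier insulin or does not know continues. One who picks the option of not using the pen is terminated after question 14.
- Questions 15 and 16: no display rule, so 16C is shown.

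A never-user thus reaches 16C unless they take the non-use exit at question 9. In the HCP survey (Appendix I.1), questions 20 and 21 are not displayed when question 11 is 0. The patient survey has no equivalent rule.

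**2. The plan's own precision figure.** Section 5.7, Equation 1: half-width = 1.96 × √[p(1 − p)/n]. With p = 0.80 and n = 280 this is 1.96 × √(0.16/280) = 4.7 points, as in Table 1. The other four rows also reproduce, so the arithmetic of Table 1 is not in question.

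**3. Effect of mixing.** Let s be the never-user share, p_u the Yes rate in users and p_n the Yes rate in never-users. Pooled rate = (1 − s)p_u + s·p_n, and shift = s(p_n − p_u). The documents give none of these three values. I assume p_u = 80%, let p_n run from 0 to 100%, and vary s:

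| s (assumed) | Pooled rate, p_n = 0 | Pooled rate, p_n = 100% | Shift (points) |
|---|---|---|---|
| 2% | 78.4% | 80.4% | −1.6 to +0.4 |
| 5% | 76.0% | 81.0% | −4.0 to +1.0 |
| 10% | 72.0% | 82.0% | −8.0 to +2.0 |
| 20% | 64.0% | 84.0% | −16.0 to +4.0 |

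In the least favourable case (p_n = 0) the shift exceeds the 4.7-point half-width once s is above 4.7/80 = 5.9%.

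**4. Cost of restricting 16C to users.** n = 280(1 − s), half-width at 80%:

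| s (assumed) | n | Half-width (points) |
|---|---|---|
| 5% | 266 | 4.8 |
| 10% | 252 | 4.9 |
| 20% | 224 | 5.2 |

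For example, 1.96 × √(0.16/252) = 4.9. Keeping 280 users at s = 10% would take 280/0.9 = 311.1, so 312 completed surveys.

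**5. The fill criterion.** Questions 1 to 14 contain no item on a fill and none on a 90-day window, although Section 5.6 lists one. The window ends at survey launch in Section 5.6, while Sections 5.2 and 5.4.1 give no reference date.

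**The case against.** The strongest reply is that the protocol already handles most of this, and much of it stands.

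- *A reader might infer that the fill criterion is unverified.* For invited patients it is applied through pharmacy records: the PBM selects on fills, mails the invitations, and access needs a single-use code. That is firmer than recall.
- *A reader might infer that never-users are ineligible or that lapsed users pass through.* Section 5.4.1 requires a fill, not use, so a patient who has filled but not injected is eligible. Questions 8 and 9 both terminate people who say they do not use the pen.
- *A reader might infer that late responders fall outside the window.* With collection planned from August to November 2016, a fill may be well over 90 days old at response. It still qualifies under the launch-anchored wording of Section 5.6.
- *A reader might infer that patients will be recruited without a fill check.* Section 5.4 says "Additional recruitment methods may be explored prior to and or during survey launch if necessary to achieve a total of 280 completed surveys". It names no non-PBM source and waives no check; it only leaves the matter open.
- *16C can be answered by anyone who injects insulin.* It refers to the respondent's own insulin, question 5 removes those not using injectable insulin, and Sections 4 and 5.5 frame behaviour partly as prospective. But the item names the U-200 safety information, and Section 5.3 ties the endpoint to administration of that pen.
- *The denominator belongs to an analysis plan.* Because question 8 is collected, a plan not shown here could restrict 16C to users. This limits the harm. The survey flow, however, is fixed in this protocol, and it puts the item to people for whom it does not apply.

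**Conclusion.** The point holds for the patient behaviour endpoint. As the survey is laid out, 16C is put to respondents who say they have not used the pen, with no answer that fits them and with Yes as the keyed response. Unless the analysis excludes them, the estimate is taken partly in people outside the behaviour it describes.

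The size is unknown and so is the direction. The 10% illustration (72% to 82% around 80%) rests wholly on an assumed share and an assumed user rate, so a definite downward bias cannot be claimed. Nor does the point reach the primary objective: never-users can validly answer 15A, 15B, 16D and 16E.

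The missing fill question is a secondary inconsistency between Sections 5.4.1 and 5.6 and Appendix I.3. It does not show that ineligible patients are surveyed.

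**What to change.** 1. Do not display 16C when question 8 is answered as not yet used, mirroring the rule on HCP questions 20 and 21; or keep the display and report 16C among users only, with the number excluded. Keep never-users in the understanding items. Check that question 9 does not end the survey for some of them and not others.
2. Reconcile Sections 5.4.1 and 5.6 with Appendix I.3. Either state that the 90-day fill is verified from PBM data and remove it from the list of screening questions, or add a question anchored to survey launch. A question asking about the 90 days before response would terminate patients who are eligible under Section 5.6. Apply the same check to anyone recruited by additional methods.

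The cost is one skip rule or one footnoted denominator, plus a wording change, before launch. Precision on 16C falls slightly (4.7 to 4.9 points at 80% under a 10% share). Nothing changes for the understanding items or the target of 280.

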5.6.1. Data collection process

The Internet survey will be self-administered. For the telephone survey, a trained interviewer from the Survey Coordinating Center will conduct the telephone interviews using a CATI program and enter participant responses directly into the Electronic Data Capture (EDC) System while in conversation with the respondent. Questions are programmed to ensure that they are asked in the appropriate sequence and skip patterns are clearly indicated. Respondents cannot go back to a question once the question has been answered and they cannot skip ahead. Statements requiring response and response options presented in a list are randomized to minimize positional bias.

5.7. Study size

The target sample sizes for the HCP and patient populations are 280 completed surveys for each population. The size of the sample was determined based on both practical and statistical considerations. There is no target comprehension rate specified *a priori*. A sample of 280 completed surveys for both HCPs and patients will allow estimation of the comprehension rate for each key safety message with a moderately high degree of precision. The table below shows the precision of the estimates for level of understanding using two-sided 95% CIs obtained with the sample size of 280 completed surveys. The noted CIs are used to indicate that for any survey-estimated rate of understanding, the true population rate of understanding is at least as high as the lower limit of the 95% CI and may be as high as the upper limit of the 95% CI.

Equation 1

$$95\%CI = Response\ Rate \pm 1.96 \left\{ \sqrt{\left[\frac{Response\ Rate(1-Response\ Rate)}{Sample\ Size} \right]} \right\}$$

Table 1 Sample size calculations

Sample Size	Observed Response Rate* (e.g. Knowledge)	2-Sided 95% CI		
		Half-width	Lower Limit	Upper Limit
280	50%	5.9%	44.1%	55.9%
	60%	5.7%	54.3%	65.7%
	70%	5.4%	64.6%	75.4%
	80%	4.7%	75.3%	84.7%
	90%	3.5%	86.5%	93.5%

*Percentage of responders who correctly answered a question.

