5.9. Data analysis

Data collected from the survey will be reported as descriptive statistics. Frequency distributions with 95% CIs will be calculated for respondent responses to all questions that address the survey objectives. Responses to each question relating to the key safety messages will be categorized as “Correct response” and “Incorrect response”. “I don’t know” is categorized as an incorrect response unless otherwise specified.

In addition to the overall analysis, survey data will be analyzed to determine if there are any differences for HCPs, by medical specialty.

The following will be reported as part of the analysis:

HCPs:

Survey administration

- The number of survey invitations issued by method of distribution and specialty

- The number of survey invitations returned due to incorrect mailing address of HCPs invited to participate in the survey
- The number of HCPs who responded to the invitation to participate in the survey
- The number of HCPs eligible for participation in the survey
- The number of ineligible HCPs along with the reasons for ineligibility
- The number of eligible HCPs who completed the survey

Demographic characteristics of participants

- Distribution of participants by age groups
- Distribution of participants by gender
- Distribution of participants by practice setting
- Distribution of HCP by state
- Distribution of participants by medical specialty
- Distribution of participants by years in medical practice
- Distribution of participants by number of patients treated with Humalog U-200 KwikPen

Responses to questions pertaining to the survey objectives:

- Awareness of the DHPC on the correct use of Humalog U-200 KwikPen
- Understanding of the key safety messages
- Self-reported practices with respect to communication of the key safety messages in clinical practice

Patients:

Survey administration

- The number of invitations distributed
- The number of survey invitations returned due to incorrect mailing address of patients invited to participate in the survey
- The number of patients who responded to the invitation to participate in the survey
- The number of patients eligible for participation in the survey
- The number of ineligible patients along with the reasons for ineligibility
- The number of eligible patients who completed the survey

Demographic characteristics of participants

- Distribution of participants by age groups
- Distribution of participants by gender
- Distribution of patient by state

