STATEMENT	Correct Response
Humalog® U-200 KwikPen® is approved for transfer to syringe or pump.	FALSE
The dose of insulin does not need to be converted when changing patients from one Humalog strength to the other (for example, changing a patient from Humalog U-100 units/ml to Humalog® U-200 KwikPen®).	TRUE
When prescribing Humalog® U-200 KwikPen®, it is important to clearly indicate the correct strength on the prescription.	TRUE
It is important to instruct your patients that they should always have a backup pen available	TRUE

If you have questions or are unclear about any of these responses, please refer to the Direct HealthCare Professional Communication for Humalog® U-200 KwikPen®.

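### Section 5.7 reads the lower 95% confidence limit as a guaranteed floor for the true rate; a confidence interval gives no such guarantee, and under the stated formula the floor fails more often than nominal at high rates.

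*Protocol*

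**What the plan says.** Section 5.7 sizes each survey on precision: "The target sample sizes for the HCP and patient populations are 280 completed surveys for each population". Equation 1 is the observed rate plus or minus 1.96 times the square root of rate × (1 − rate) / n, that is, the Wald interval. Table 1 applies it to show "the precision of the estimates for level of understanding using two-sided 95% CIs obtained with the sample size of 280 completed surveys", for observed rates of 50%, 60%, 70%, 80% and 90%. No target rate is set. The section then explains how the limits are to be read: for any rate the survey estimates, "the true population rate of understanding is at least as high as the lower limit of the 95% CI".

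Section 5.9 commits to intervals in the results: "Frequency distributions with 95% CIs will be calculated for respondent responses to all questions that address the survey objectives". It names no method. It also plans to look for differences between HCP specialties, without giving group sizes and without saying that intervals will be shown by specialty. Section 5.10 says the tables follow a survey analysis plan, which is not shown.

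Section 5.3 judges the measures effective if a majority of respondents are aware of the messages, with no hypothesis test. Section 5.6 says descriptive statistics and confidence intervals will be used to determine effectiveness. Section 5.11 acknowledges that respondents are self-selected.

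**The concern.** The sentence turns a statement about the long-run behaviour of a procedure into a certainty about one estimate. With no target rate and no test, the estimates and their intervals are all the inference this study offers, so the meaning given to the lower limit matters. The error runs in one direction: it makes understanding of the safety messages look more firmly established than it is.

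The formula beside the sentence makes this worse at high rates. The Wald interval is symmetric about the observed rate and shrinks to nothing as that rate approaches 100%, so its lower limit is too high too often there. Some items invite agreement, for example "When prescribing Humalog® U-200 KwikPen®, it is important to clearly indicate the correct strength on the prescription". Rates close to 100% are plausible for these, although the protocol gives no expected rate for any item.

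**Working it through.** **Inputs.** n = 280, z = 1.96 and Equation 1, all from Section 5.7. The item structure and the cap on HCPs without treated patients come from Appendix I.1. The true rates below are illustrative, because the protocol gives none.

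**Step 1: reproduce Table 1.** Half-width = 1.96 × √(p(1 − p)/280).

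| Observed rate | Half-width, recomputed | Limits, recomputed | Table 1 |
|---|---|---|---|
| 50% | 5.86 | 44.1–55.9 | 5.9; 44.1–55.9 |
| 60% | 5.74 | 54.3–65.7 | 5.7; 54.3–65.7 |
| 70% | 5.37 | 64.6–75.4 | 5.4; 64.6–75.4 |
| 80% | 4.69 | 75.3–84.7 | 4.7; 75.3–84.7 |
| 90% | 3.51 | 86.5–93.5 | 3.5; 86.5–93.5 |

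Every row agrees. The Wilson interval in the 90% row is 85.9–93.0, at most about 0.6 point away. Exact Wald coverage at n = 280 is 95.2%, 94.3% and 94.6% at true rates of 50%, 80% and 90%. For planning over this range the formula is adequate.

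**Step 2: how often the claimed floor is false.** For a true rate π, find the smallest count whose Wald lower limit exceeds π, then sum the binomial(280, π) probabilities from that count upward.

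| True rate | Smallest count with lower limit above it | P(true rate < lower limit) | Wald coverage |
|---|---|---|---|
| 50% | 157 | 2.4% | 95.2% |
| 90% | 261 | 4.0% | 94.6% |
| 95% | 272 | 5.7% | 93.5% |
| 98% | 278 | 8.0% | 91.5% |
| 99% | 280 | 6.0% | 93.8% |

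The 98% row can be checked by hand. The lower limit is 97.7% at 277/280 and 98.3% at 278/280, so the floor fails at 278, 279 and 280: 5.68% + 2.00% + 0.35% = 8.0%. In the 99% row only 280/280 fails: 0.99^280 = 6.0%. The nominal figure for one side is 2.5%. Even a method that met its nominal level would not make the limit a certain bound.

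**Step 3: what Equation 1 would give if it were used for reporting.**

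| Correct of 280 | Wald | Wilson | Clopper-Pearson |
|---|---|---|---|
| 266 (95.0%) | 92.4–97.6 | 91.8–97.0 | 91.8–97.2 |
| 277 (98.9%) | 97.7–100.1 | 96.9–99.6 | 96.9–99.8 |
| 279 (99.6%) | 98.9–100.3 | 98.0–99.9 | 98.0–100.0 |
| 280 (100%) | 100–100 | 98.6–100 | 98.7–100 |

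At 276/280 the Wald upper limit is 99.96%, so it first passes 100% at 277. At 280/280, the sentence in Section 5.7 read with Equation 1 would assert a true rate of 100%.

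**Step 4: a smaller denominator that the survey itself can create.** In Appendix I.1, Questions 20 and 21 (the HCP behaviour items) are not shown to respondents who answer 0 to Question 11. That group is capped at a configurable 140 completers. If the cap fills, 280 − 140 = 140 HCPs answer these items. Wald coverage at n = 140 is then 91.3% at a true rate of 95% and 75.5% at 99%. The second figure arises because 140/140 alone has probability 0.99^140 = 24.5% and gives a lower limit of 100%. At 140/140 the Wilson and exact lower limits are 97.3% and 97.4%.

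**The case against.** The strongest reply is that Equation 1 is planning text. It sits in the study-size section beside a table of sample-size calculations, its arithmetic is right, and over 50% to 90% it performs well. Section 5.9 does not call on it, and the interval method for output tables is commonly left to the analysis plan that Section 5.10 mentions. All of this stands. A reader might infer from Equation 1 being the only formula that the reported limits will be degenerate or too narrow. The protocol does not support that: it describes what would happen if Equation 1 were carried into reporting, and nothing says that it will be.

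A reader might also infer serious undercoverage in specialty groups. Group sizes are not given, and intervals by specialty are not promised, so no figure can be attached to that. The 140 in Step 4 is better grounded, but it depends on a configurable cap filling.

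It is also fair that near-ceiling rates are an expectation, that self-selection is already disclosed in Section 5.11, and that a majority criterion would not turn on a shift of about one point near the top of the scale.

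The reply does not rescue the sentence itself. Section 5.7 applies it to any estimated rate, it carries no confidence qualifier, and it is false whichever interval method the analysis plan names.

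**Conclusion.** The interpretation sentence in Section 5.7 is wrong and should be corrected. Its size under Equation 1 at n = 280 is a one-sided failure rate of 4.0% to 8.0% at true rates of 90% to 98%, where 2.5% is nominal. These figures assume simple binomial sampling from the target population. Self-selected response adds error that no sampling interval covers.

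The choice of reporting method is a conditional, advisory point: it matters only if Equation 1 is reused and observed rates are near 100% or denominators fall. At n = 280 the shortfall in coverage is modest, about 1 to 3.5 points at true rates of 95% to 99%. Table 1 and the sample size stand, and the majority-based conclusion is unlikely to change. Severity: minor.

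**What to change.** 1. In Section 5.7, replace the interpretation sentence with: *With 95% confidence, and assuming respondents represent the sampled population, the population rate lies between the limits; this does not cover non-response bias.*
2. Label Equation 1 and Table 1 as planning only.
3. In Section 5.9, state that reported 95% intervals for proportions are Wilson score or Clopper-Pearson, choosing one, for every denominator on which an interval is shown.

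The cost is a few sentences and one software option. At n = 280 some lower limits become less favourable by about 0.6 point at 90% (86.5 to 85.9) and up to 1.4 points at 280/280 (100 to 98.6, Wilson). No further recruitment is needed.
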